**PROTOCOL SYNOPSIS**

STUDY TITLE	A phase 3, open-label, randomized, multicenter, 12 months, efficacy and safety study of weekly MOD-4023 compared to daily Genotropin ® therapy in pre-pubertal children with growth hormone deficiency.		
PROTOCOL NO.	CP-4-006, Amendment 2, 27-APR-2018		
IND NO.	CCI	EUDRACT NO.	2016-003874-42
CLINICAL SITES	The study will be conducted in approximately 30-40 countries at approximately 200 clinical sites.		
STUDY PHASE	3		
THERAPEUTIC INDICATION	Treatment of children with growth failure due to growth hormone deficiency (GHD).		
STUDY PRIMARY OBJECTIVE	To demonstrate that weekly MOD-4023 administration is non-inferior to daily Genotropin administration.		
STUDY SECONDARY OBJECTIVES	
 
• To evaluate the safety and tolerability of weekly MOD-4023 administration.
 
• To demonstrate successful operation (single injection) of the MOD-4023 single patient use, multi-dose, disposable pre-filled pen (PEN).
 
• Evaluation of participant and observer feedback on MOD-4023 device usability.
 
• To confirm the correct operation of devices returned for evaluation.
 
		
LT-OLE OBJECTIVE	To demonstrate long term (LT) safety and efficacy of MOD-4023 in an open-label extension (OLE).		
OTHER OBJECTIVES	To evaluate the effect of weekly MOD-4023 and daily Genotropin ® administration on quality of life (QoL), as measured by the QoLISSY (Quality of Life in Short Stature Youth) in a specific number of countries (determined by availability of validated translated tools) during the first 12 months of treatment.		
STUDY DESIGN	
The study will initially consist of a 12 month, open-label, randomized, active controlled, parallel group study comparing the efficacy and safety of weekly MOD-4023 to daily growth hormone (GH), Genotropin®. Patients will enter a long term open-label extension to demonstrate continued safety and efficacy of MOD-4023 treatment (all patients) after successful completion of the first 12 months of treatment.
 
Initial Study Period (main study): After a screening period lasting up to 8 weeks (wks), patients meeting the eligibility criteria, as approved by the Global Study Medical Monitor (MM), will be randomized in a 1:1 ratio to MOD-4023 or Genotropin® for 12 months.
 
If the patient's screening process is delayed because of a benign illness or unforeseen benign condition (i.e. pharyngitis, viral gastrointestinal (GI) problems, minor accident or trauma, etc.) or a technical issue that is related to screening procedures (for example, delays with lab results), extra time will be added to the duration of the screening period, but not in excess of an additional 4 wks (total of 12 wks).
 
An independent and external Data and Safety Monitoring Board (DSMB) will review the key safety data approximately every 4 months or on ad hoc basis.
		

Effective Date: Date of final electronic approval

	
LT-OLE Period (LT-OLE): Patients who received MOD-4023 during the main study will continue in the LT-OLE with the same dose (mg/kg/wk) of MOD-4023. Patients who received Genotropin® during the main study will be switched to MOD-4023 and will begin treatment with a dose of 0.66 mg/kg/wk beginning no less than one day after cessation of Genotropin® treatment. The key safety data will be reviewed by an independent DSMB approximately every 6 months. During the entire study, doses will be adjusted based on the patients' body weight every 3 months. The dose may be decreased or maintained for safety reasons according to the pre-defined dose-adjustment criteria (based on the severity of adverse events [AEs] or repeated, elevated levels of insulin-like growth factor -1 [IGF-1] Standard Deviation Score [SDS]).


STUDY PROCEDURES
	
Visit 1 - Screening Period (Day -56 to Day -1)
 
The Screening period will last up to 8 wksa and can be conducted over several visits prior to eligibility approval and randomization. Screening visits are intended to collect current clinical data and to perform all required investigations needed to establish a patient's eligibility for the study. Prior to any study-specific investigations, written assent from pediatric patients (where applicable based on age and country) and consent from the parent(s) or legal guardian(s) will be obtained.
 
The following assessments will be conducted at these screening visits:
 
 
• Inclusion/exclusion verification.
 
• Parental heightsb (Ht), and patients' Ht, Ht SDS, Ht velocity (HV) and HV SDS.
 
• Body weight and body mass index (BMI) SDS.
 
• Medical history, including a description of pituitary deficiencies, concomitant and previous medications.
 
• Overall health status assessment, including complete physical examination and vital signs.
 
• Pubertal status (according to Tanner stages).
 
• Bone age (BA) determination according to the method of Greulich-Pyle using a central BA readerc.
 
• Assessment of biochemical markers and stimulation testsd:             
 
○ Two different GH stimulation (provocation) tests: insulin tolerance test (ITT) (with serum cortisol response to
 
 
 

a If the patient's screening process is delayed because of a benign illness or unforeseen benign condition (i.e. pharyngitis, viral GI problems, minor accident or trauma, etc.) or a technical issue that is related to screening procedures (for example, delays with laboratory results), extra time will be added to the duration of the screening period, but not in excess of an additional 4 wks (total of 12 wks screening period).

b It's recommended that parents' Ht be measured at the site. If measured parental Ht is not available an estimate should be provided by the parent.

c Historical BA assessment might be accepted if it was done according to the method of Greulich-Pyle no more than 6 months prior to the informed consent form (ICF) signature date. If the patient is eligible, the BA must be repeated at Visit 2 prior to dosing. The Visit 2 scan will be the baseline scan for these patients.

d Local, documented provocation tests that were performed prior to ICF signature, might be accepted by the global study MM according to his/her judgment.

e ITT with serum cortisol response to hypoglycemia is adequate for assessment of adrenal insufficiency and no ACTH stimulation test is required if such results are available. Historical ACTH test is acceptable.

Effective Date: Date of final electronic approval

	
hypoglycemia if insulin stimulation test is chosen)/arginine test/clonidine test/glucagon test/L-dopa test.
 
 
○ Analysis of serum GH levels (and glucose and serum cortisol if ITT is performed) may be performed by local laboratories and must be provided for global MM review and approval.
 
○ Assessment of morning cortisol (at 8 am ± 1 hour)             
 
▪ If morning cortisol is below 190 nmol/L (7 µg/dL), test for adrenal insufficiency will be required – low dose adrenocorticotrophic hormone (ACTH)e or corticotropin releasing hormone (CRH) stimulation test (only if the patient was not previously assessed for the hypothalamus-pituitary-adrenal axis or has been diagnosed with adrenal insufficiency).
 
 
 
○ Assessment of IGF-1, IGF-1 SDS, IGF binding protein-3 (IGFBP-3) and IGFBP-3 SDS levels.
 
 
 
• Assessment of anti-human GH (hGH) antibody (Ab) levels.
 
• Assessments of routine safety: chemistry, hematology and urinalysis.
 
• Assessment of thyroid function tests (thyroid stimulating hormone [TSH], free thyroxine [FT4]).
 
• Assessment of glucose metabolism (overnight fasting insulin, overnight fasting glucose and glycated hemoglobin [HbA1C]).
 
• Head magnetic resonance imaginga (MRI), if possible with contrast or computed tomography (CT) scan.
 
• Assessment of karyotype in girlsb.
 
• SHOX (short stature homeobox) gene evaluationc. Patients with confirmed multiple pituitary hormone deficiencies or confirmed structurally abnormal pituitary gland or other anatomical reasons for GHD do not require SHOX gene evaluation. SHOX gene evaluation is mandatory for isolated GHD with normal brain MRI.
 
 
All laboratory assessments are performed by a central laboratory unless stated otherwise.
 
Key data and all test results obtained during screening will be reviewed by the Global Study MM and eligibility will be confirmed prior to randomization of each patient. It is recommended that the Investigator randomize the patient within 7 days of confirmed eligibility.
 
Main Study Treatment Period (Day 1/Baseline to Month 12)
 
Eligible patients will be randomized (centralized randomization within each region) in a 1:1 fashion to receive either weekly MOD-4023 or daily Genotropin® for 12 months.
 
The following 3 stratification factors will be applied when randomizing patients to the treatment groups:

--	---

a Historical MRI or CT is permitted if within 12 months prior to ICF signature date. For GHD associated with a congenital central nervous system (CNS) defect, the global study MM could allow for use of the historic MRI or CT > 12 months old.

b Historical karyotype data and chromosomal microarray data are acceptable.

c Historical data is acceptable.

Effective Date: Date of final electronic approval

	
 
• Region:             
 
1. Western Europe, Israel, Australia, New Zealand, Canada and USA;
 
2. Central and Eastern Europe, Greece, Turkey, Latin America and Asia, except for India and Vietnam;
 
3. India and Vietnam.
 
 
 
• Peak GH levels (<math>\leq 3</math> ng/mL; <math>>3</math> to <math>\leq 7</math> ng/mL; and <math>>7</math> to <math>\leq 10</math> ng/mL). The proportion of patients with peak GH levels <math>>7</math> to <math>\leq 10</math> ng/mL, will be capped at 35-40% of total sample-size, in the randomization scheme.
 
• Chronological age (CA) (<math>\geq 3</math> years to <math>\leq 7</math> years, 0 days; and <math>>7</math> years, 0 days)
 
 
During main study, patients will be scheduled for clinic visits at Visit 2 (Baseline/Day 1, first dose – no more than 2 wks post randomization), Visit 3 (Day 10ab; 10+4 days post first dose), and at Wk 4 (1 month), 3 months and every 3 months thereafter (up to 12 months).
 
Visit 2 (Day 1/Baseline) will be conducted on day of first dosing– no more than 2 wks post randomization, Visit 4 (Month 1/Wk 4 [+1 wk]), Visit 5 Month 3/Wk 13 [<math>\pm 1</math> wk]), Visit 6 (Month 6/Wk 26 [<math>\pm 1</math> wk]), Visit 7 (Month 9/Wk 39 [<math>\pm 1</math> wk]), and Visit 8 (Month 12/Wk 52 [<math>\pm 1</math> wk]) will be conducted on day 4 (-1 day) post dose to obtain IGF-1 measurements expected to reflect average levels of IGF-1 throughout the wk.
 
The following assessments will be obtained at these visits:
 
 
• Auxology measurements (excluding Visit 3 and Visit 4): Actual Ht (average of three consecutive measurements) measured on a calibrated wall mounted stadiometer.
 
• AEs, local tolerability, and concomitant medications (on site or by phone) (all visits).
 
• Overall health status assessment, including complete physical examination and vital signs assessment (excluding Visit 3).
 
• Safety laboratory tests (excluding Visit 3): chemistry, hematology and urinalysis.
 
• Pubertal status (according to Tanner stages) (excluding Visits 3 and 4);
 
• Urine pregnancy test at every visit once a female patient reports first menstrual cycle (menarche) (excluding Visits 3 and 4).
 
• Assessment of thyroid function (excluding Visits 3 and 4): TSH, FT4.
 
• Assessment of biochemical markers (excluding Visit 3): IGF-1, IGF-1 SDS, IGFBP-3 and IGFBP-3 SDS serum levels.
 
• Assessment of MOD-4023 serum levels (applicable for MOD-4023 arm only) (Visits 2, 3, 4, 5, 6a, 7 and 8a).
 
• Parameters of glucose metabolism (excluding Visits 3 and 4): overnight fasting glucose, overnight fasting insulin, HbA1c.
 
• Parameters of lipid metabolism (excluding Visits 3 and 4): overnight
 

--	---

a Applicable only for MOD-4023, Visit 3 assessments, if conducted on Day 14 (dosing day), should be performed **prior** to dosing.

b Blood samples for MOD-4023 treatment group can be collected at site OR at patient's home, based on local regulations and nurse availability. If home visit, a questionnaire, as described in [Appendix I](#), should be completed. If blood sample is collected on Day 14, it should be obtained **prior** to dosing.

Effective Date: Date of final electronic approval

	
fasting cholesterol, triglycerides, high density lipoprotein (HDL), low density lipoprotein (LDL), lipoprotein a (Lp(a)), Free Fatty Acids (FFA).
 
 
• For males that are 13 years and older: Luteinizing Hormone (LH), Follicle-Stimulating Hormone (FSH) and testosterone. For females that are 12 years and older: LH, FSH and estradiol (Visit 8 only).
 
• Assessment of anti-MOD-4023 Ab (MOD-4023 arm) at Visits 2, 3, 4, 5, 6a, 7, 8a.
 
• Assessment of anti-hGH Ab (Genotropin® arm) at Visits 2, 4, 5, 6, 7 and 8 only.
 
• BA assessments at Visits 1, 2 (at Visit 2 only if historical data was provided for eligibility evaluation and not performed as part of Visit 1) and Visit 8 only.
 
• Fundoscopy (if there are signs or symptoms indicative of benign intracranial hypertension).
 
• ECG at Visit 2 for all patients, pre- dosing and ECG on Visit 6 for patients treated with daily Genotropin®. All MOD-4023 patients will undergo an ECG during Visit 6b, 7-12 hours post dosing.
 
• USA Only - The Participant Assessment Tool (PAT) completed at Wks 1, 2, 3, 4, 5 and 6 for MOD-4023 treated patients. In any given wk a new PAT will be completed for each PEN used that wk (in some cases more than 1 PEN may be used for full dose administration, in which case a PAT will be completed for each PEN used that wk. In some cases, more than 1 injection from the same PEN may be needed, in which case only 1 PAT is completed for that PEN that wk).
 
• USA Only - The Observer Assessment Tool (OAT) completed at Wk 1 for MOD-4023 treated patients. A new OAT will be completed for each PEN used (in some cases more than 1 PEN may be used for full dose administration, in which case an OAT will be completed for each PEN used. In some cases, more than 1 injection from the same PEN may be needed, in which case only 1 OAT is completed for that PEN). Wk 1 corresponds to study Visit 2, which will be at the site.
 
• Individual dose adjustment every three months based on weight.
 
• Drug dispensing Visits 2, 4, 5, 6, 7 and 8 (for patients entering the LT-OLE).
 
• QoL questionnaire (Visits 2 and 8 only); patients below the age of 7 and 0 days will be completing the questionnaire with their parents/legal guardians using a parent questionnaire while patients above and including the age of 7 and 0 days will be encouraged to use the child questionnaire. The QoL questionnaire will be completed in specific countries (determined by availability of validated translated tools) as described in Appendix L.
 
 
For MOD-4023 patients arm only, Visit 3 (Day 10 [+4 days] post first dose), Visits 6a (Month 6/Wk 26 [<math>\pm</math>3 wks]) and Visit 8a (Month 12/Wk 52 [<math>\pm</math>1 wk]) will be conducted on dosing day, blood samples will be taken pre-dose for assessment of MOD-4023 serum levels. These blood samples can be collected at site OR at patient's home, based on local regulations and nurse availability. If home visit, a questionnaire as described in Appendix I should be completed.
 
For Genotropin® patients on Day 10 (+4 day) post first dose a phone interview will be conducted according to the questions as provided in Appendix I.

--	--

Effective Date: Date of final electronic approval

For ECGs that will be conducted at Visit 6b, Month 6/Wk 26 ( $\pm$  3 wk) at Time 7-12 hours post-dose for MOD-4023 treated patients, patients will be requested to inject MOD-4023 during the day/night at their convenience and come to the study site at the requested time point for ECG.

Visit 6a and 6b may be combined on the same day (only if 6a is done prior to dosing).

Genotropin® patients will have an ECG assessment at Visit 6 (no time limitation, however date and time of the assessment will be recorded).

Both MOD-4023 and Genotropin® treated patients will be required to complete a patient diary card at home or at site (if injection done on site). MOD-4023 injected patients will complete the patient diary after every injection to collect data on AE, concomitant medications and local injection site reactions.

Genotropin® injected patients will complete a patient diary once a wk (preferably on the same day of the wk, each wk) to collect data on AE, concomitant medications and local injection site reactions.

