REFERENCE THERAPY	
Genotropin® is a daily GH, and is used as the reference therapy in this study. A delivery device (Genotropin® Pen) will be used for daily (evening/bedtime) SC administration of Genotropin® into the region of the upper arms, buttocks, thighs or abdomen (8 locations). Injection sites should be rotated.
 
Starting dose regimen for Genotropin®: 0.034 mg/kg/day (which is equivalent to 0.24 mg/kg/wk divided equally into 7 daily injections).
 
IGF-1 SDS will be monitored throughout the study, and if a patient has an IGF-1 level above +2.0 SDS, they will be requested to return for an unscheduled visit within 4-6 wks after the > +2.0 SDS result, on any day post dose (for Genotropin® treated patients). If their IGF-1 level is still above +2.0 SDS, the most recent dose will be reduced by 15%. They will continue to be monitored for any further dose reduction.

MAIN STUDY ENDPOINTS	
Primary efficacy endpoint:
 
 
• Annual HV in cm/year after 12 months of treatment.
 
 
Secondary efficacy endpoints (Auxology/Clinical):
 
 
• Annualized HV after 6 months of treatment.
 
• Change in Ht SDS at 6 and 12 months, compared to baseline.
 
• Change in bone maturation (BM) at the end of 12 months, compared to Baseline BAa (calculated as BA/CA).
 
 
Secondary endpoints (Biochemical):
 
 
• Absolute IGF-1 and IGF-1 SDS levels on Day 4 (-1) after MOD-4023 dosing across study visits.
 
• IGFBP-3 levels and IGFBP-3 SDS on Day 4 (-1) after MOD-4023 dosing across study visits.
 

SAFETY ENDPOINTS	
 
• Incidence of AEs and serious adverse events (SAEs).
 
• Incidence of anti-MOD-4023 Ab formation (including characterization of the Ab and neutralizing properties).
 
• Local injection site reaction assessment.
 
• Parameters of glucose metabolism: blood fasting glucose, fasting insulin level, HbA1c.
 
• Thyroid (endocrinology) status.
 
• Lipid profile.
 
• All other safety hematology, biochemical parameters and urinalysis.
 
• Physical examination.
 
• Vital signs.
 
• Fundoscopy results- if performed (normal/abnormal).
 
• ECG.
 

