#### 5.2.6 Visit 6a (Month 6/Wk 26 [ $\pm 3$ wk]) and Visit 8a (Month 12/Wk 52 [ $\pm 1$ wk]) – MOD-4023 Arm Only

Visit 6a and 8a will be conducted on dosing day before dosinga, for MOD-4023 arm patients only. The following assessments will be conducted at the study site or at the patient home (if allowed according to local regulations):

- MOD-4023 serum levels.
- Anti-MOD-4023 Ab.
- AEs and local tolerability (aligned with Appendix H) assessment.
- Concomitant medication recording aligned with the questionnaire in [Appendix I](#).

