#### 5.8.2 Local Tolerability (Injection Site Reactions)

Assessment of local tolerability will be performed by examining the injection sites (by the investigator if a reaction is present at the time of every visit, excluding Visit 1) and on the basis of anamnestic data and records in the patient diary. Observations of local injection site reactions will be recorded on the appropriate eCRF pages.

The patients and parents/legal guardians will be trained to record, at least once weekly, any injection site reaction in their diaries.

An abnormal injection site reaction is defined as:

- Injection site reaction which is reported or observed at the time of visit or during a phone call and is of moderate to severe in intensity.
- Injection site reaction between the last and present visit or remaining at the time of visit which require medical attention, or injection site reaction resulting from a previous injection, other than the last injection.
- Any other injection site reaction deemed abnormal to the investigator's judgment, other than those ordinarily observed in subcutaneous injections.
- Pain score  $\geq 4$  (as reported in the patient diary).

If an injection site reaction meets the criteria for "abnormal" defined above, it will be considered and assessed as an AE.

- Pain: For patients, injection site pain will be evaluated by the investigator or designated personnel if the injection is given at the medical center, and by the parent/legal guardian if the injection is given at home. The pain will be evaluated at least once weekly using a Pain Rating Scale and recorded in the patient diary. In addition, each patient and parent/guardian will be queried during study visits regarding possible injection site pain.
- Pain score  $\geq 4$  should be reported as an AE.

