## APPENDIX A: STUDY FLOW CHART / SCHEDULE OF EVENTS

### Main Study

Study Procedure	Screening		Baseline	Treatment								Follow-up b	
Study Day ( $\pm$ in dy/s)	a -56 to -1		1/	10 (+4)							EOS b		
Study Wk ( $\pm$ in wk/s)	-8 to -1 (+4) a		0 (+4 from Eligibility)		4 (+1)	13 ( $\pm$ 1)	26 ( $\pm$ 1)	26 ( $\pm$ 3)	26 ( $\pm$ 3)	39 ( $\pm$ 1)	52 ( $\pm$ 1)	52 ( $\pm$ 1)	56 ( $\pm$ 5 days)
Study Month	-2		0	0.5	1	3	6	6	6	9	12	12	13
Study Visit	1		2	3	4	5	6	6a c	6b	7	8/10 d	8a c /10 d	9
Informed consent	X									X e	X f		
Inclusion/exclusion criteria	X										X e		
Demographic & medical history including parent Ht	X												
Auxology measurements g	X		X			X	X			X	X		
Physical examination and vital signs h	X		X		X	X	X			X	X		
ECG			X pre-dose				X i		X j				
Pubertal status (Tanner stages)	X		X			X	X			X	X		

a For the screening period, additional 4 wks might be added due to technicalities or patient's benign illness.

b If ET during the main study or **not** continuing to LT-OLE.

c Dosing day (assessments will be conducted pre-dose). This visit is applicable only for patients in MOD-4023 arm.

d Visit 8 if EOS at completion of the main study, Visit 10 if continuing to LT-OLE.

e If continuing to LT-OLE.

f Informed consent for the LT-OLE may be obtained at Visit 7 or Visit 8.

g Actual Ht (mean of 3 consecutive measurements per patient per visit) measured on a calibrated wall mounted stadiometer.

h Body weight, ideally fasted in the morning, without shoes and having removed all outwear and heavy pocket items.

i Genotropin® patients.

j ECG will be conducted at 7-12 hours post-dose (MOD-4023 arm only). Patients will be requested to inject MOD-4023 during the day/night at their convenience and come to the clinic at the requested time point for ECG.

Effective Date: Date of final electronic approval

Study Procedure	Screening		Baseline	Treatment								Follow-up b	
Study Day ( $\pm$ in dy/s)	a -56 to -1		1/	10 (+4)							EOS b		
Study Wk ( $\pm$ in wk/s)	-8 to -1 (+4) a		0 (+4 from Eligibility)		4 (+1)	13 ( $\pm$ 1)	26 ( $\pm$ 1)	26 ( $\pm$ 3)	26 ( $\pm$ 3)	39 ( $\pm$ 1)	52 ( $\pm$ 1)	52 ( $\pm$ 1)	56 ( $\pm$ 5 days)

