**Pain Assessment**

The patients will be asked to point to the face that best describes the pain they are experiencing (in the patient diary) and circle the corresponding number.

Effective Date: Date of final electronic approval

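### The weekly Genotropin diary entry has no stated recall window for injection-site pain, while MOD-4023 is rated after every injection and has one or two extra AE enquiries

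*Protocol*

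**What the plan says.** **Diary.** The Protocol Synopsis (Study Procedures, main study) gives each arm its own rule. For the weekly product, "MOD-4023 injected patients will complete the patient diary after every injection to collect data on AE, concomitant medications and local injection site reactions". For the daily product, Genotropin "injected patients will complete a patient diary once a wk (preferably on the same day of the wk, each wk", and that page collects the same three kinds of data. The Synopsis (Reference Therapy) gives the comparator schedule as "0.24 mg/kg/wk divided equally into 7 daily injections".

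**Common minimum.** Section 5.8.2 has families in both arms record any reaction at least weekly. For pain it says: "The pain will be evaluated at least once weekly using a Pain Rating Scale and recorded in the patient diary". A score of 4 or more is an AE. Each family is also asked about injection-site pain at study visits.

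**Pain scale.** Appendix H (Pain Assessment) asks the child to "point to the face that best describes the pain they are experiencing". It gives no look-back period.

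**Extra visits.** Section 5.2.6 states: "Visit 6a and 8a will be conducted on dosing day before dosing", for the MOD-4023 arm, with AE and local tolerability assessment at each. Section 5.2 pairs the MOD-4023 Visit 3 with a Genotropin phone interview (Appendix I) but describes no such call for 6a or 8a. In Appendix A, footnote c on 6a and 8a reads "This visit is applicable only for patients in MOD-4023 arm", while footnote r, attached to the 8a cells for AEs and local tolerability, describes a phone interview for the Genotropin arm.

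**Use of the data.** Local injection-site reaction is a safety endpoint (Section 8.4.4). AEs are summarised as patient incidence by treatment group (Section 8.6.7).

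**The concern.** A pain score that reaches the threshold becomes an AE, so how often pain is rated, and over what period, affects the AE tables. One arm has an entry for each injection; the other has one entry for seven injections, and the protocol does not say whether that entry describes today's injection, the worst of the week, or something between. Sites and families may settle this differently. Two columns that look alike in the safety tables could then rest on different measurements.

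The MOD-4023-only enquiries at 6a and 8a add a second, smaller difference: more scheduled occasions on which an event can be elicited in one arm.

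What is at stake is how fairly the descriptive injection-site and AE tables compare weekly with daily injection. The primary analysis of height velocity is not touched.

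**Working it through.** The documents give no figure for completeness of tolerability recording, so there is nothing to reproduce. The check is a count of entries, injections and enquiries from the schedules.

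**1. Diary entries against injections, per patient over 52 weeks**

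Inputs: one MOD-4023 dose a week (Section 6.3; split doses ignored), seven Genotropin injections a week (Synopsis), and the Synopsis diary rules.

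| | MOD-4023 | Genotropin |
|---|---|---|
| Injections | 1 × 52 = 52 | 7 × 52 = 364 |
| Diary entries | 52 | 52 |
| Entries / injections | 52/52 = 100% | 52/364 = 14.3% |
| Injections without their own entry | 0 | 364 − 52 = 312 (85.7%) |

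At 110 randomized per arm with full adherence, 110 × 312 = 34,320 of 110 × 364 = 40,040 Genotropin injections would have no entry of their own.

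**2. What the weekly Genotropin score may mean**

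- *Diary-day reading:* the score describes one injection. One injection in seven is rated, against every MOD-4023 injection.
- *Whole-week reading:* coverage is 52 of 52 weeks in both arms, but a seven-day recall is set beside a rating made after a single injection.

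The Appendix H wording leans to current pain. The Section 5.8.2 instruction on reactions leans to the whole week. Neither settles the pain score.

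**3. Illustration of the diary-day reading at its extreme**

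Assume the same probability p of a score of 4 or more at each injection in both arms, independence between injections, and no capture route except the diary. The chance of at least one event in k injections is 1 − (1 − p)^k. The values of p are assumed; the documents give none.

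| p (assumed) | Recorded, either arm (k = 52) | True for Genotropin (k = 364) |
|---|---|---|
| 0.1% | 5.1% | 30.5% |
| 0.5% | 22.9% | 83.9% |
| 1% | 40.7% | 97.4% |

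This is a worst case. Correlation within a child and the other capture routes would shrink the gap by an amount the documents do not let us calculate. Only the direction carries over: the comparator is under-recorded.

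**4. Scheduled AE enquiries, Visits 2 to 8a (Appendix A)**

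- MOD-4023: Visits 2, 3, 4, 5, 6, 6a, 7, 8, 8a = 9.
- Genotropin: Visits 2, 3 (phone), 4, 5, 6, 7, 8 = 7, or 8 if footnote r governs at 8a.
- Difference: 9 − 7 = 2, or 9 − 8 = 1.

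Appendix A also marks local tolerability at the MOD-4023-only Visit 6b, although Section 5.8.1 leaves 6b out. If it counts, the difference for local tolerability is 2 to 3.

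**The case against.** A reader might infer that the plan misses most comparator injections. The documents do not support that. It follows only if each weekly entry rates a single injection, and Section 5.8.2 asks for all reactions at least weekly. The same page also collects AEs and concomitant medications, which suggests a look back over the week. The diary card itself was not supplied and may contain a prompt that the protocol does not show.

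Other routes also bring events in. Families are asked about pain at visits. Reactions between visits that need medical attention count as abnormal (Section 5.8.2). New AEs between visits are to be reported (Section 5.8.1). The Appendix I call asks about injection-site changes over recent weeks.

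A reader might also treat weekly-against-daily tolerability as a formal objective. The secondary objective in Section 2 concerns MOD-4023 alone, and safety data are to be listed and tabulated (Section 8.6.6). Nor should the asymmetry be read as favouring the new product: under-recorded comparator pain and extra MOD-4023 enquiries both tend to make MOD-4023 look worse. Even that direction is not certain for reactions, because Section 5.8.2 also counts as abnormal a reaction left by an injection before the last, a condition a daily product can meet sooner.

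The extra contacts are few. Visit 3 is matched, and 6a and 8a fall near Visits 6 and 8, when both arms are asked about AEs. A weekly page in place of some 364 daily entries is also a reasonable choice for children.

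All of this limits the size of the problem. It does not supply the missing recall window, make the two ratings alike, or resolve the conflict between footnotes c and r.

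**Conclusion.** The point stands in limited form. The diary rule differs by arm, and the protocol does not state which injections the weekly Genotropin pain score covers. On one reading, one injection in seven is rated; on the other, recall is compared with a rating made after a single injection. Either way the arms are measured differently, and injection-site pain may be under-recorded under Genotropin.

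The 14.3% rests on full adherence, no split doses and the diary-day reading; it is a ratio of entries to injections, not an estimate of missed events. The bias in reported AE incidence cannot be sized from the documents. The extra MOD-4023 AE enquiries number one or two, and nothing supplied shows how far they change AE counts.

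The supplied SAP covers only the LT-OLE, and Section 8.5 assigns the main study to a separate SAP, so the unit in which main-study reactions will be summarised cannot be checked. The change is worth making because it is cheap and brings the two arms' tables closer to a common basis.

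**What to change.** 1. Word the weekly Genotropin entry to ask for the worst pain score and any reaction across all injections since the last entry, and state this look-back in Section 5.8.2 and Appendix H.
2. In the main-study SAP, summarise injection-site results in both arms as the proportion of patient-weeks with any reaction or a pain score of 4 or more. Give per-injection rates second, with their denominators.
3. Use the Appendix I phone interview for Genotropin patients at the times of Visits 6a and 8a. Alternatively, flag events first elicited at MOD-4023-only visits and show the AE summary without them.
4. Reconcile Appendix A footnotes c and r for Visit 8a.

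Cost: a small diary and protocol change, one week of recall on the Genotropin page, and up to two short calls per Genotropin patient (at most 2 × 110 = 220). Flagging instead of calling avoids the calls. A recalled weekly maximum is still not identical to a rating after one injection, so the report should say so; the gain is that both arms then cover all injections and share a unit.
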